6.3 Subgroup analyses

A KM analysis of time to platelet count response (primary endpoint) in function of treatment group (Caplacizumab, Placebo) will be performed separately for the following subgroups:

- ADAMTS13 activity at admission or baseline: < 10% / ≥ 10%
- Previous TTP episode(s): initial / recurrent
- Severity of disease at baseline category: very severe / less severe

Each subgroup analysis will only be conducted if at least 5 data points are available by subgroup in each treatment group.

[figure not shown]
The number and proportion of subjects with refractory TTP by treatment group (Caplacizumab, Placebo) will be summarized for the following subgroups:

- ADAMTS13 activity at admission or baseline: < 10% / \geq 10%
- Previous TTP episode(s): initial / recurrent
- Severity of disease at baseline category: very severe / less severe

The number and proportion of subjects with recurrence by treatment group (Caplacizumab, Placebo, OL Caplacizumab) in the overall treatment period and in the overall study period will be summarized by severity of disease at baseline category (very severe / less severe).

The number and proportion of subjects with at least one treatment-emergent major thromboembolic event, confirmed after adjudication, by treatment group (Caplacizumab, Placebo, OL Caplacizumab) in the overall treatment period will be summarized by severity of disease at baseline category (very severe / less severe).

6.4 Exploratory analyses

Term	Percentage
GMOs	95
Organic	90
Natural	85
Artificial	75
Organic	70
Natural	65
Artificial	60
Organic	55
Natural	50
Artificial	45

7 SAFETY

All analyses will be run on the safety population.

7.1 Adverse Events

7.1.1 Methods and definitions

All adverse events will be coded using the latest version of the Medical Dictionary for Regulatory Activities (MedDRA).

All adverse events starting or worsening in severity (for pre-existing conditions) from the start of study drug administration until completion of the subject's last visit are considered treatment-emergent adverse events (TEAE).

Adverse events will be placed into analysis periods (phases, periods and subperiods) according to their start date(time). The AE will only be presented in the analysis period during which it started, i.e. period start date(time) \leq AE start date(time) \leq period stop date(time). There will be no imputation of other missing date(time) fields, nor of the missing parts of other partially known date(time) fields. When needed (e.g., an incomplete date(time) leads to a double phase allocation), the following rules will be applied: adverse events will be allocated on all analysis levels (i.e., for analysis phases, periods and subperiods, see Section 4.4) according to their start date(time). In case the adverse event (AE) start date(time) is incomplete, the allocation will be done according to the available parts of the AE start date(time) and taking into account the AE end date(time) (i.e., the AE start date(time) cannot be later than the AE end date(time)):

- When, due to missing date(part) an allocation needs to be made to an analysis phase, the AE will be allocated to the treatment phase and not the screening or follow-up phase (worst-case allocation).
- When an allocation needs to be made within the treatment phase to an analysis period, the AE will be allocated to the double-blind treatment period.
- When an allocation needs to be made within an analysis period, the event will be allocated to the daily PE subperiod.

CONFIDENTIAL

If the AE start date is completely missing but AE end date and study drug administration are non-missing and AE end date is before the first study drug administration and after signing ICF, then the AE is defined as pre-treatment. All adverse events emerging during the screening period will only be listed and will not be presented in any of the tables. These events are not TEAEs. All tables will thus present TEAEs only.

According to ICH-E3, the drug relatedness as assessed by the investigator will be dichotomized as follows:

- Drug-related: at least possibly drug-related, OR with a missing drug-relatedness (= worst-case).
- Not drug-related: less than possibly drug-related.

In tabulations this dichotomized drug-relatedness will be used, but in the listings the original drug-relatedness will be presented.

Relationship to PE and relationship to corticosteroids are collected as related or not related. Missing relatedness will be considered as related.

When cross-tabulating AE preferred terms versus an AE attribute (e.g., severity), the worst-case is always applied within each analysis period. This means that when a subject has the same AE preferred term twice in the same analysis period, then the subject is reported only once: with the worst severity. If this happens in two different analysis periods, the subject is reported twice: once in each analysis period.

AE onset day and AE duration are defined as follows:

- AE onset day
 - = AE start date – date of first study drug intake + 1 day (when the AE start date is completely known)
 - = missing (when the AE start date is incomplete or unknown).
- AE duration
 - = AE stop date – AE start date + 1 day (when both dates are completely known)
 - = trial termination date – AE start date + 1 day (when the AE start date is fully known but the AE is not resolved at the end of the trial): in this case the duration will be presented as “>x days” in the listing rather than “x days”
 - = missing (when the AE start date is incomplete or unknown, or when the AE has resolved but with an incomplete or unknown end date).

These derived parameters will only be presented in the listings. Note that the start and stop times of the AE are not used.

All percentages will be calculated against the total number of subjects (within each treatment group) that are still in the study in that particular analysis period.

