4.3.6 Presentation of treatment groups

The following treatment group labels will be used in the tables, listings and figures, unless specified otherwise:

- Caplacizumab
- Placebo
- Open-label (OL) Caplacizumab

Treatment groups Caplacizumab and Placebo refer to the initial treatment group prior to a potential switch to open-label caplacizumab, and only data up to the switch are used in the analyses of these treatment groups. The OL Caplacizumab treatment group will only be used for analyses after the switch to open-label caplacizumab.

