7.1.2 Analysis

The following analysis periods will be considered for all AE tables:

- DB treatment daily PE period
- DB treatment post-daily PE period
- OL treatment daily PE period
- OL treatment post-daily PE period
- Overall treatment period
- FU period
- Overall study period

Summaries on AEs will be presented by treatment group (Caplacizumab, Placebo, OL Caplacizumab, Caplacizumab Total) and by analysis period. The 'Caplacizumab Total' group will combine events that have occurred for all caplacizumab-treated subjects. For subjects who received placebo in the DB treatment period, only events after switch to open-label caplacizumab will be counted for the Caplacizumab Total group.

A general summary table will be presented by treatment group and analysis period, reporting the number and percentage of subjects, the number of events and the incidence per 100 patient months, which will be calculated as: $100 \times (\text{Number of subjects with AE}) / (\text{Total number of months observed within analysis period, summed for all subjects})$. The following categories will be included in the summary table:

- Subjects with at least one TEAE
- Subjects with at least one serious TEAE
- Subjects with at least one TEAE leading to death
- Subjects with at least one TEAE for which the study drug was interrupted
- Subjects with at least one TEAE for which the study drug was withdrawn
- Subjects with at least one TEAE that was considered at least possibly treatment-related by the investigator
- Subjects with at least one serious TEAE that was considered at least possibly treatment-related by the investigator
- Subjects with at least one bleeding event, i.e. an event documented as event indicating an increased bleeding tendency
- Subject with at least one bleeding event, based on the Standardized MedDRA Query (SMQ) 'Haemorrhage terms (excluding laboratory terms)'
- Subjects with at least one thromboembolic event, based on the SMQ 'Embolic and thrombotic events (arterial, venous, and vessel type unspecified and mixed arterial and venous)'
- Subjects with at least one hypersensitivity reaction, based on the SMQs 'Hypersensitivity' (Narrow), 'Anaphylactic reaction' (Narrow) and 'Angioedema' (Narrow)
- Subjects with at least one hypersensitivity reaction, based on the SMQs 'Hypersensitivity' (Narrow), 'Anaphylactic reaction' (Narrow) and 'Angioedema' (Narrow), considered at least possibly treatment-related by the investigator.

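### SAP 7.1.1 counts worsening after first dose as treatment-emergent but places adverse events by start date only, so an event that worsens on one open record can be missing from the period, and column, where it worsened

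*SAP*

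**What the plan says.** SAP 7.1.1 gives the definition of a TEAE: "All adverse events starting or worsening in severity (for pre-existing conditions) from the start of study drug administration" until the last visit. The same section allocates each event to an analysis period by its start date and time, and adds "The AE will only be presented in the analysis period during which it started". For events before dosing it says "All adverse events emerging during the screening period will only be listed and will not be presented in any of the tables", and the next sentence declares that these events are not TEAEs. No rule refers to a date of worsening. The rules for incomplete dates do not help, because the question arises for events with complete dates.

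Treatment columns follow the same timing. SAP 4.3.6 says of the Caplacizumab and Placebo groups that "only data up to the switch are used in the analyses of these treatment groups". SAP 7.1.2 says that, for subjects who had placebo first, "only events after switch to open-label caplacizumab will be counted for the Caplacizumab Total group". On severity, SAP 7.1.1 says "the worst-case is always applied within each analysis period", but it has no rule for a severity that changes from one period to the next.

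On recording, protocol 3.5.1 treats an aggravation from baseline as an adverse event, and has conditions that deteriorate after consent documented as adverse events. It also asks for an onset time, an end time and a severity rating for each entry. It does not say whether an event already open is closed and re-entered when its severity rises.

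**The concern.** The definition recognises worsening, but the placement rule has no means of using it. Bleeding is where this matters most. Protocol 1.2.5 names it as the main safety finding, and protocol 1.2.4 reports bleeding-related TEAEs in 54.3% of caplacizumab and 37.8% of placebo subjects in Phase II. Petechiae, epistaxis and bruises are among the signs assessed at screening, so some subjects may have a minor bleeding event open at first dose. If such an event becomes severe on study drug, a reader of the tables should be able to see it.

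The switch raises a similar question. A bleed that is mild on blinded placebo and severe after open-label caplacizumab says something about caplacizumab, but neither column that describes open-label exposure would show it.

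Protocol 3.5.1.3 adds a further loss. Causal relation to study drug is to be marked not applicable for events that start before dosing, so worsening kept on such a record also has no causality assessment.

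Two programmers who both follow SAP 7.1.1 could produce different TEAE tables.

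**Working it through.** No figure in the plan depends on this rule, so the check is to apply the rules to cases. Period boundaries are from SAP 4.4.1: screening ends one minute before the first double-blind dose, and the open-label period begins at the first open-label dose. Each case is run under the two recording conventions that the documents leave open.

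| Case | Same record kept open | New record at worsening |
|---|---|---|
| Starts after consent and before first dose, worsens on Day 3 | Screening: listed, in no table | Worsened part tabulated in the double-blind arm received |
| Starts on double-blind placebo, worsens after the switch | Placebo only | Placebo, plus OL Caplacizumab and Caplacizumab Total |
| Starts on double-blind caplacizumab, worsens after the switch | Caplacizumab and Caplacizumab Total, not OL Caplacizumab | All three columns |

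In the first row, middle column, the definition makes the event a TEAE and the screening sentence says that it is not one. That is the contradiction. In the second and third rows nothing is contradicted. The event is already a TEAE from its double-blind onset, and the SAP has no separate definition of treatment emergence for the open-label period, although SAP 4.3.1 does reset baseline for that period.

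Which severity the Placebo row would show in the second case is also unsettled. SAP 4.3.6 limits that column to data before the switch, but an entry with a single severity rating may hold only the later, worse grade.

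For scale, take 132 subjects randomised 1:1, so 66 per arm (protocol synopsis). The documents give no switch rate, so two assumptions set a range:

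- Phase II on-treatment exacerbation rates, 28% placebo and 8% caplacizumab (protocol 1.2.4): 0.28 × 66 = 18.5 and 0.08 × 66 = 5.3 switchers, so an open-label group of 23.8.
- Design rates for the first key secondary composite, 30% and 10% (SAP 3.2), taken as an upper bound because recurrence is only one component: 0.30 × 66 = 19.8 and 0.10 × 66 = 6.6, so an open-label group of 26.4.

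One misplaced placebo switcher, with no other event in the same table row, then changes the percentages as follows:

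- OL Caplacizumab: 100/23.8 = 4.2 points, or 100/26.4 = 3.8 points.
- Caplacizumab Total: 100/(66 + 18.5) = 1.2 points, or 100/(66 + 19.8) = 1.2 points.

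For comparison, one subject in the Placebo column is 100/66 = 1.5 points. The documents give no rate of worsening after first dose or after the switch, so the calculation stops at one subject.

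**The case against.** The strongest reply is that the loss depends on recording practice. If sites open a new record when severity rises, its start date is the date of worsening and every case above is tabulated where it should be. A reader might infer that the SAP ties an event to its first onset whatever the record structure. It does not; it says only start date. Protocol 3.5.1 also ensures that a condition present before consent which later deteriorates becomes an adverse event. This stands as a limit on the concern. It does not remove it, because that text separates medical history from adverse events and does not cover an event already open. The eCRF completion guidelines may settle the matter, but neither document quotes them.

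A reader might also infer bias in favour of caplacizumab. The documents do not support that. The screening exclusion is the same for both arms. A bleed that starts on placebo is correctly counted in Placebo incidence; what can go wrong is its severity there and its absence from the open-label columns. For subjects who switch from blinded caplacizumab, worsening in the open-label period stays attached to double-blind Caplacizumab. More placebo than caplacizumab switchers are expected on Phase II rates, but no net direction follows.

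A reader might scale the problem up from Phase II event totals. Only events still open at first dose or at the switch can be affected, and the documents do not give their number. The pre-dose window is usually short: protocol 3.3.6 allows at most 24 hours between the start of the first plasma exchange and the start of the first on-study exchange, and the loading dose precedes the latter. Clinically significant active bleeding is an exclusion criterion.

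Finally, every event remains in the listings, bleeding events have their own listing, and the DSMB reviews unblinded serious events. These safeguards are real, but comparisons between columns are made from the tables.

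**Conclusion.** The screening part of SAP 7.1.1 is wrong as written: an event that starts between consent and first dose and worsens on study drug is both included and excluded. The open-label part is a gap, because nothing says how worsening after the switch is to be counted. Either leads to an actual loss only if worsening stays on one record, which the documents leave open.

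The number affected is unknown and probably small, and no net direction of bias is shown. What can be said about size is that the open-label column is small. With an assumed 24 to 26 subjects, each misplaced subject moves its percentage by about 4 points and Caplacizumab Total by about 1.2. This rests on the assumed switch rates, on 66 treated subjects per arm, and on the subject having no other event in the same row. It is worth correcting because it bears on the main known risk and the correction is cheap.

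**What to change.** Amend SAP 7.1.1 before database lock:

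1. Confine the statement that screening-onset events are not TEAEs, and their exclusion from the tables, to events that do not worsen after first dose.
2. State that an increase in severity after first dose, or after the first open-label dose, is counted as a TEAE at the worsened severity in the period and treatment column where it worsened. This can be done through a new adverse event record dated at the worsening, or by allocation on the date of worsening.
3. State that the earlier period keeps the earlier severity.
4. Align SAP 4.3.6 and 7.1.2 with this, so that worsening after the switch enters OL Caplacizumab and Caplacizumab Total.

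The cost is a few sentences in the SAP, a note in the eCRF completion guidelines on how worsening is entered, and a limited query of events ongoing at first dose or at the switch. No design figure or efficacy analysis changes.

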Study drug treatment extension beyond these 30 days will be guided by a number of risk factors for relapse of the presenting TTP episode and must be accompanied by an optimization of the immunosuppressive treatment. The risk factors will include the ADAMTS13 activity profile (measured weekly), as well as other signs and symptoms of continued underlying disease activity, such as presence of inhibitors if measured as routine practice by the site. Continued study drug treatment should be given for additional 7-day periods with a maximum of 28 days for subjects whose ADAMTS13 activity profile remains below 10% based on weekly measurements and for subjects with other clinical signs of underlying disease. In parallel, optimization of the immunosuppressive treatment should be considered starting at the Week 3 visit of the 30-day post-daily PE period and includes reversal of corticosteroid tapering through increase or re-initiation of corticosteroid treatment, or start/continuation of other immunosuppressive treatment such as rituximab (to be used as per standard site practice). Study drug treatment extension should be stopped when ADAMTS13 activity shows a sustained upward trend of >10% and at the latest on Day 28 of the study drug treatment extension.

Recurrence of TTP episode

- Exacerbation is defined as recurrent thrombocytopenia after initial recovery of platelet count (platelet count $\geq 150 \times 10^9/L$ with subsequent stop of daily PE within 5 days), requiring re-initiation of daily PE, occurring during the first 30-days post-daily PE period.
- Relapse is defined as recurrent thrombocytopenia after initial recovery of platelet count requiring re-initiation of daily PE, occurring after the 30-days post-daily PE period.

Based on the mechanism of action and the available efficacy and safety results from study ALX-0681-2.1/10 (Phase II TITAN trial) it is considered desirable from both a treatment and exposure perspective (to maximize the number of subjects exposed to caplacizumab), to allow for crossover to open-label caplacizumab for subjects who experience a recurrence of the TTP episode.

Exacerbation

In case of a first exacerbation of the presenting TTP episode, subjects will receive open label caplacizumab together with daily PE irrespective of what the initial treatment allocation was.

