4.4 Analysis Periods and Visit Windows

4.4.1 Analysis periods

The following analysis phases are defined for this study: Screening, Treatment, Follow-up. Within these analysis phases, the following analysis periods and subperiods will be considered:

Table 1: Analysis periods

Period	Subperiod	Start period	End period
(Screening)		Date of signing the ICF, with 00:00 added as timepart	First DB treatment administration datetime – 1 min
Double-Blind (DB) Treatment	Daily PE	First administration datetime of DB treatment	Start of DB post-daily PE subperiod – 1 min
	Post-daily PE	Date of switch to post-daily PE + 1 day with 00:00 added as timepart	Min(Week 5 visit date if no treatment extension or last visit date of treatment extension period with 23:59 added as timepart, early termination visit date with 23:59 added as timepart, first administration datetime of OL treatment – 1 min)
	Daily PE	First administration datetime of OL treatment	Start of OL post-daily PE subperiod – 1 min

CONFIDENTIAL

Open-label (OL) Treatment	Post-daily PE	Date of switch to post-daily PE + 1 day with 00:00 added as timepart	Min(Week 5 visit date if no treatment extension or last visit date of treatment extension period, early termination visit date) with 23:59 added as timepart
(Follow-up)		End of treatment period + 1 min	Trial termination date, with 23:59 added as timepart

Note that the last analysis period in case of early termination will always be ended by the trial termination date.

The 'overall treatment period' corresponds with the treatment analysis phase and covers both the DB treatment analysis period and the OL treatment analysis period. Note that only subjects who experience a relapse or exacerbation will have an OL treatment analysis period. For these subjects, the overall treatment period starts at start of DB treatment period and ends at end of OL treatment period. For subjects with no switch to open-label caplacizumab, the overall treatment period starts at start of DB treatment period and ends at end of DB treatment period.

The 'overall study period' covers both the treatment analysis phase and the follow-up analysis phase.

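### In placebo subjects who switched, adverse events that could have begun on either side of the switch are counted under Placebo and left out of the caplacizumab columns

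*SAP*

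**What the plan says.** SAP 7.1.1 places each adverse event in an analysis period by its start date and time. If the start is incomplete, the known parts of the start and the end date are used first. Three tie-breaking bullets follow for events still unresolved:

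- Between phases, treatment is preferred to screening or follow-up. This bullet is labelled worst case.
- Between periods within the treatment phase, "the AE will be allocated to the double-blind treatment period". This bullet has no such label and no rationale, and it does not depend on arm.
- Within a period, the event goes to the daily plasma exchange subperiod.

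The same section treats missing drug-relatedness as related, and says that this is worst case.

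The columns of the safety tables are defined elsewhere. For the Caplacizumab and Placebo groups, "only data up to the switch are used in the analyses of these treatment groups" (SAP 4.3.6). For the pooled column, "For subjects who received placebo in the DB treatment period, only events after switch to open-label caplacizumab will be counted for the Caplacizumab Total group" (SAP 7.1.2). The double-blind period ends one minute before the "first administration datetime of OL treatment" (SAP 4.4.1).

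The switch is to active drug in both arms. At a first exacerbation, "subjects will receive open label caplacizumab together with daily PE irrespective of what the initial treatment allocation was" (Protocol synopsis). The same holds for a first relapse during the treatment extension.

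**The concern.** A tie-breaking rule for dates should not lean towards the investigational drug. For a placebo subject who switched, the two candidate periods differ in treatment: placebo before, caplacizumab after. Sending every unresolved event to the earlier period can add events to Placebo, and can remove from OL Caplacizumab and Caplacizumab Total events that in fact began on caplacizumab. The SAP plans no analysis with the opposite allocation.

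The boundary is a clock time, so a known date without a time on the day of the switch is enough to leave the period open. Bleeding is the main known safety finding for the drug (Protocol 1.2.5), and the open-label column will be small, so a few subjects could visibly change a percentage.

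**Working it through.** The plan states no figure on this point, so the check traces the rule and then sizes one misallocated subject.

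**Tracing an event that fits both periods**

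| Subject | Period given by SAP 7.1.1 | Counted under | Not counted under |
|---|---|---|---|
| Placebo, switched | Double-blind | Placebo | OL Caplacizumab, Caplacizumab Total |
| Caplacizumab, switched | Double-blind | Caplacizumab, Caplacizumab Total | OL Caplacizumab |
| Never switched | No choice arises | Own arm | – |

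Only the first row takes an event away from the drug altogether.

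**How many subjects are in the first row**

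Inputs: 132 adults randomized 1:1, so 66 per arm (SAP 3.1). Phase II on-treatment exacerbation was 28% on placebo (11 of 39) and 8% on caplacizumab (Protocol 1.2.4).

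- Placebo: 0.28 × 66 = 18.5, or 11/39 × 66 = 18.6.
- Caplacizumab: 0.08 × 66 = 5.3.
- Upper guide from the sample-size rates for the composite endpoint, 30% and 10% (SAP 3.2): 0.30 × 66 = 19.8 and 0.10 × 66 = 6.6, so about 20 and 7. It is an upper guide because not every composite event is a recurrence. With 66 per arm these rates give 82.7% power, which agrees with the stated figure of approximately 83%.

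**What one misallocated subject does to the percentages**

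Take 20 and 7 switchers. The denominators are Placebo 66, OL Caplacizumab 20 + 7 = 27, and Caplacizumab Total 66 + 20 = 86. Suppose a placebo switcher's event truly began after the switch, and the subject has no other event of that kind in either period. The present rule then changes the columns as follows:

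- Placebo: +1/66 = +1.5 points
- OL Caplacizumab: −1/27 = −3.7 points
- Caplacizumab Total: −1/86 = −1.2 points
- Caplacizumab Total minus Placebo: narrowed by 1.52 + 1.16 = 2.7 points

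**Illustration with bleeding**

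Use the Phase II proportions with a bleeding-related event (54.3% caplacizumab, 37.8% placebo; Protocol 1.2.4) as if they were the true rates. The true gap is 16.5 points. The number k of misallocated subjects is an assumption.

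| k | Placebo | Caplacizumab Total | Gap (points) |
|---|---|---|---|
| 0 | 37.8% | 54.3% | 16.5 |
| 1 | 39.3% | 53.1% | 13.8 |
| 2 | 40.8% | 52.0% | 11.1 |
| 3 | 42.3% | 50.8% | 8.5 |

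**Counting events instead of subjects**

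Phase II had 545/37 = 14.7 treatment-emergent events per placebo subject. If 1% to 5% of events had an unresolved period (assumed; no document gives a rate), 18.5 × 14.7 × 0.01 to 0.05 = 2.7 to 13.6 events would be reallocated. The upper end is generous. The formula lets any of a subject's events straddle the switch, and some of those counted truly began on placebo.

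**The case against.** Four objections deserve an answer.

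**Reach.** A reader might infer that every event with an incomplete date goes to double-blind. The text does not say that: the known date parts and the end date are used first, and only subjects who switched can be affected. Collection also limits ambiguity. Protocol 3.5.1 asks for onset and end times, and subjects are expected to be in hospital during daily plasma exchange and are seen weekly afterwards. This stands, and it is why the effect is probably small.

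**Direction.** A reader might infer that the rule raises Placebo and lowers caplacizumab throughout. The documents do not support this. The rule is the same in both arms. In caplacizumab switchers it can raise the double-blind Caplacizumab column, and it never lowers it. The columns that can fall are OL Caplacizumab and Caplacizumab Total, which are not randomized comparisons. This stands too. What remains is that only placebo switchers lose events from Caplacizumab Total, and that placebo subjects are expected to switch more often.

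**The opposite rule has its own error.** The recurrence that triggers the switch is always reported as a serious adverse event (Protocol 3.4.8.1) and by design begins before the first open-label dose. If its clock time is missing, the present rule places it correctly. A blanket reversal would charge a placebo subject's recurrence, and its presenting symptoms, to caplacizumab. This stands, and any replacement rule needs an exception for it.

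**Visibility.** All events are listed with their dates and period limits (SAP Listing 16.2.7.1), and the SAP does not call the period bullet worst case. For the overall count of subjects with any event, Phase II had 100% on placebo, so at that rate the percentage could not rise. These points are fair, but a listing does not correct a summary table, and narrower categories such as bleeding can still move.

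**Conclusion.** The point holds in a limited form. For placebo subjects who switched, the period rule in SAP 7.1.1 is not worst case for the drug, unlike the handling of phase and relatedness beside it. It bears on the Placebo, OL Caplacizumab and Caplacizumab Total columns of the safety tables. No efficacy test or power figure is affected.

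The group at risk is about 18 to 19 of 66 placebo subjects, if the Phase II rate recurs. Each misallocated subject with no other such event narrows the difference between Caplacizumab Total and Placebo by about 2.7 points, on the assumed 20 and 7 switchers. How many such subjects there will be cannot be derived from the documents. The bleeding table shows sensitivity and is not a forecast. The documents do not support a claim that the safety comparison as a whole is biased, or any firm count of displaced events.

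**What to change.** Add one sentence to SAP 7.1.1. For subjects randomized to placebo who switched, an event whose known dates fit both periods is allocated to the open-label caplacizumab period, except the recurrence that triggered the switch and its presenting symptoms, which stay in double-blind. Keep the present rule for all other subjects, and report the number of events allocated this way. Which events count as presenting symptoms should be settled before unblinding.

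The alternative is to keep the rule as it is and add one sensitivity table with the opposite allocation, together with the count.

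Either change affects the analysis only, with no new data and no change to treatment. The cost is a sentence and some programming. The first option may slightly overstate events on caplacizumab, which is what a worst-case rule accepts, and it makes the allocation depend on arm. The second avoids both drawbacks in the main tables.
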